### **3.2 Primary Effectiveness Endpoint**

It is the Technical Success, the ability of the BridgePoint Medical System to successfully facilitate placement of a guidewire beyond a CTO lesion in the true vessel lumen/within the collaterals

The primary endpoint is summarized with counts and percentage and based on binomial proportion 95% CI will be presented for successfully facilitate placement of a guidewire and thus summarized. The endpoint will be analyzed based on both ITT and PP population definitions.

#### **3.2.1 Hypotheses**

There is no specific hypothesis planned for this study.

#### **3.2.2 Sample Size**

The study planned to enroll 100 patients with CTO lesions and will use BridgePoint Medical CTO System for treatment.

#### **3.2.3 Statistical Methods**

For Calculating the Primary Effectiveness, the discontinuous variables (percentage and number of events / number of samples) of baseline and clinical outcome variables will be summarized by descriptive statistics and for continuous variables (mean, standard deviation, observation number, minimum and maximum, 95% Confidence Interval) will be calculated.

### **3.3 Secondary Endpoint**

The Secondary endpoints will be analyzed for all subjects at 30day, 6months, 12months and a one year follow up will be done for:

- Procedural success is a mean lesion diameter stenosis <50% in 2 near-orthogonal projections with TIMI 2-3 flow, as visually assessed by the physician, without the occurrence of in-hospital Q wave MI, TLR, or cardiac death.
- Total procedure time
- Total Fluoroscopy time and dose (mSv)
- Total contrast dose
- rate of MACE at 30 days, 6 months and 12 months
- rate of stent thrombosis (ST) at 30 days, 6 months and 12 months
- rate of cardiac tamponade through hospital discharge after the index procedure
- rate of kidney failure caused by contrast through hospital discharge after the index procedure

Secondary endpoint analysis are analyzed with both Intent to treat and per-protocol analysis and summarized with counts and percentage and based on binomial proportion 95% CI will be presented.

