10.1 Point of Enrollment

If a subject signs an IRB/IEC approved informed consent form (ICF) and meets all inclusion criteria and fails to meet any exclusion criterion, it is considered that this subject is eligible to be enrolled into this study. The point of inserting any BridgePoint CTO device(s) into the body of the subject is the formal enrollment time point of this subject.

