11.7 Enrollment and Index Procedure

Use the standard catheter puncture technique to perform the procedure. The time of inserting the first guiding catheter is the start time of the procedure.

During the procedure, the following operation and assessment shall be completed:

- coronary artery angiography: all patients shall receive angiography assessment in the procedure according to standard clinical routine practice. Angiography data and films of enrolled subjects , as well as working records of technical personnel shall be submitted to Angiographic Core Laboratory for qualitative and quantitative analysis, including the confirmation of the guidewire's entry into the vessel subintimal. Angiography data and films of intervention on

non-target vessel in the index procedure do not need to be submitted to Angiographic Core Laboratory.

- Confirm the lesion meets the inclusion criteria of angiography and fails to meet any exclusion criterion of angiography.
-
- When BridgePoint CTO device facilitates a guidewire to cross the target lesion and the guidewire is confirmed to locate in the true vessel lumen or distal collateral branch vessel lumen of target lesion, all subjects shall receive PCI treatment on the target lesion according to local clinical practice, such as using balloon catheters to make pre-dilation, stent implantation, etc., to target lesion.

In this study, before the failure of BridgePoint CTO System device, other devices against CTO (such as Frontrunner, Crosser or SafeCross, etc.) shall not be used, but the intravascular ultrasound-guided true-lumen seeking and tracking (IVUS-TST) is allowed, i.e., the technique in which the guidewire can cross (or re-cross) the true lumen and move forward along the true lumen to the distal vessel under the guidance of IVUS and taking the occluded segment as the target.

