11.8 End of Procedure / Prior to Hospital Discharge

The end time of procedure is defined as the time of removing the guiding catheter (after the final angiography). The following steps shall be completed after removing the catheter sheath according to local clinical routine practice:

- Record information of target lesion, guidewire and balloon catheter used, and information of pre-dilation, post-dilation (if applicable) and stent implantation and other information on corresponding eCRFs.
- Record procedure information on corresponding eCRFs, including start and end time of procedure, total fluoroscopy time of X-ray, total contrast dose used in the procedure, etc.
- Collect current cardiac medications: collection is only required for subjects with any changes of cardiac medications.
- Record anticoagulation and antiplatelet medications during the procedure.
- As described in section 24, complete recording and assessment of adverse events in the procedure and and collect source documents.
- 12 lead ECG within 1 day post procedure
- Laboratory detection
 - At least one CK Total or CK-MB draw must be obtained within 1 day after the index procedure. If the CK Total value is abnormal, CK-MB must be run.
 - If CK/CK-MB is not used, the troponin shall be run.

Note: it is recommended that the same type of cardiac enzymes shall be collected prior to and after the procedure during the hospitalization.

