## **4 GENERAL STATISTICAL METHODS**

### **4.1 Analysis Sets**

All primary and Secondary endpoints will be analyzed both on an intent-to-treat (ITT) basis and on a per-protocol (PP) basis.

For intent-to-treat analyses, all patients who sign the IRB/IEC-approved study ICF and are enrolled in the study will be included in the analysis, regardless of whether or not a study device was implanted.

For per-protocol analyses, only patients who signed the IRB/IEC-approved study ICF and had used any component of BridgePoint Medical CTO System will be included in the analysis.

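### SAP 3.3 counts never-stented subjects in the stent thrombosis denominator and sets no rule for N when 6- and 12-month follow-up is incomplete

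*SAP*

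**What the plan says.** - **Population and times.** SAP 3.3: "The Secondary endpoints will be analyzed for all subjects at 30day, 6months, 12months".
- **Method.** SAP 3.3: "Secondary endpoint analysis are analyzed with both Intent to treat and per-protocol analysis and summarized with counts and percentage", with a binomial 95% confidence interval. The endpoint list includes MACE and stent thrombosis at 30 days, 6 months and 12 months. It gives no denominator specific to stent thrombosis and no time-to-event method.
- **Analysis sets.** Under intention to treat in SAP 4.1, "all patients who sign the IRB/IEC-approved study ICF and are enrolled in the study will be included in the analysis", whether or not a device was implanted. The per-protocol set needs consent and that the patient "had used any component of BridgePoint Medical CTO System will be included in the analysis".
- **Enrollment.** Protocol 10.1: "The point of inserting any BridgePoint CTO device(s) into the body of the subject is the formal enrollment time point of this subject". This is before crossing or stenting is known.
- **Treatment after crossing.** Protocol 11.7 provides for PCI of the target lesion once the guidewire is confirmed in place, and stenting is one example of it: "such as using balloon catheters to make pre-dilation, stent implantation, etc., to target lesion". The ban on competing CTO devices applies only up to system failure ("before the failure of BridgePoint CTO System device, other devices against CTO").
- **Stent data.** Protocol 11.8 has sites record "information of pre-dilation, post-dilation (if applicable) and stent implantation and other information on corresponding eCRFs". Protocol 31.2 times stent thrombosis from stent implantation.
- **Incomplete follow-up.** Protocol 10.2 keeps data already collected on withdrawn subjects but follows them no further. SAP 7.3 rules out imputation, apart from a rule for missing or partial adverse event dates. SAP 5.3 tabulates follow-up compliance. Protocol 11.3.2 divides events by a number of samples that it does not define. Neither document gives a censoring rule or a definition of N at 6 or 12 months.

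**The concern.** A subject without a stent cannot have stent thrombosis. If such subjects sit in the denominator, the reported rate mixes the risk of the event with the chance of having been stented. The per-protocol analysis does not help, because it does not require a stent either.

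For the 6- and 12-month rates, two programmers could follow the SAP faithfully and report different percentages from the same data: one keeps subjects lost early in N, the other leaves them out. Neither crude rate estimates the 12-month risk when follow-up is incomplete. The protocol's own background shows how the choice of N matters. First-in-man events were reported as 3/31 = 9.7% of followed subjects (Protocol 4.1.4), whereas 44 were treated (Protocol 4.1), which would give 3/44 = 6.8%.

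The study is purely descriptive, so the estimates are the result, and SAP 2 foresees their use in manuscripts and regulatory submissions. These are its only longer-term safety figures.

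**Working it through.** SAP 3.3 states no expected rate, loss or denominator, so there is no planned figure to reproduce.

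**1. Stent thrombosis**

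Inputs: N = 100 (SAP 3.3.2); 2 events (assumed); unstented share u. The documents do not give u. I use 5% as an assumption, and technical failure in the earlier trials as a proxy:
- first-in-man: 7/44 = 16% (Protocol 4.1.3)
- FAST-CTO: (147 − 113)/147 = 34/147 = 23% (Protocol 4.3.3.4)
- EU trial: (42 − 28)/42 = 14/42 = 33% (Protocol 4.2.5.2)

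If no event is attributed to an unstented subject, the all-subject rate equals the per-stented rate × (1 − u). It is therefore lower by the fraction u. Intervals are exact (Clopper-Pearson).

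| Unstented | Events / denominator | Rate | 95% CI |
|---|---|---|---|
| as planned, all subjects | 2/100 | 2.0% | 0.2 to 7.0 |
| 5% | 2/95 | 2.1% | 0.3 to 7.4 |
| 16% | 2/84 | 2.4% | 0.3 to 8.3 |
| 23% | 2/77 | 2.6% | 0.3 to 9.1 |
| 33% | 2/67 | 3.0% | 0.4 to 10.4 |

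**2. Incomplete follow-up**

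Inputs, all assumed: true 12-month MACE p = 0.10; a fraction L = 0.10 or 0.20 lost at times spread evenly over 12 months, unrelated to risk. Let m be the mean event risk before loss among those lost.

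- Lost subjects kept in N: (1 − L)p + Lm
- Event-free losses dropped: [(1 − L)p + Lm] / [1 − L(1 − m)]

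Constant hazard: m = 1 − 0.10/(−ln 0.90) = 0.0509.
- L = 0.10: kept 0.0900 + 0.0051 = 9.5%; dropped 0.0951/0.9051 = 10.5%
- L = 0.20: kept 0.0800 + 0.0102 = 9.0%; dropped 0.0902/0.8102 = 11.1%

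Events concentrated early: 4.8 points by day 30, as in FAST-CTO (Protocol 4.3.3.3), with loss only afterwards. Then s = (0.10 − 0.048)/0.952 = 0.0546 and m = 0.048 + 0.952 × [1 − s/(−ln(1 − s))] = 0.0742.
- L = 0.10: kept 9.7%, dropped 10.7%
- L = 0.20: kept 9.5%, dropped 11.6%

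For scale, the exact 95% CI for 10/100 is 4.9 to 17.6.

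**3. Kaplan-Meier or competing risks**

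Take 10% MACE and 2% non-cardiac death at 12 months with constant hazards. The total hazard is −ln 0.88 = 0.1278, and the MACE share is 0.1278 × 10/12 = 0.1065. Kaplan-Meier with such deaths censored gives 1 − exp(−0.1065) = 10.1%, against a cumulative incidence of 10.0%. The choice hardly matters here.

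**The case against.** **The all-subject stent thrombosis rate is a legitimate quantity.** The study device is a crossing system, and risk per subject in whom it was used matches the primary safety denominator. This stands: the planned rate is not wrong. It answers a different question from risk after stenting, which the plan never reports.

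**The effects are small and attrition may be low.** Telephone visits are allowed, three calls and a registered letter are required, 12-month data are required for every subject, and compliance is tabulated. There is no hypothesis or decision threshold. This also stands and limits the weight of the point. A compliance table shows attrition but does not define N.

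Four stronger readings are tempting, and the documents do not support them.
- A reader might infer that lost subjects are scored event-free, so that both problems lower the reported rates. No section says so. Treating an unknown outcome as no event sits badly with the no-imputation rule in SAP 7.3, which can equally be read as leaving those subjects out.
- A reader might infer from Protocol 11.9.1 that a subject unreachable at 6 months must stay in the 6-month N, because final loss is declared only at the last contact. The same section also records loss at the individual contact, and it is a contact procedure that says nothing about N.
- A reader might take the request in Protocol 31.2 for cumulative stent thrombosis values as prescribing a time-to-event estimator. The sentence contrasts accumulated with separate time points, and cumulative counts over N would satisfy it.
- A reader might treat FAST-CTO's 23% technical failure as the most that could go unstented. The EU trial had 33%, and the proxy is loose both ways: a failed case may be crossed with another device or stented in another vessel, and a crossed lesion may be treated by balloon alone.

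**Conclusion.** The point holds in two parts of different strength.

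The stent thrombosis part is firm. As written, both analysis sets include never-stented subjects, and the all-subject rate falls below the per-stented rate by exactly the unstented share. Only the size is uncertain, because that share and the event count are assumptions: 2.0% against 2.1% to 3.0% over the range examined.

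The follow-up part is a missing rule rather than a bias of known direction. The crude percentage is off under either reading, down if lost subjects stay in N and up if event-free losses are dropped. The two readings differ by about 1.0 point at 10% loss and 2.1 points at 20% loss, for an assumed true rate of 10%, constant hazard and loss unrelated to risk.

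Both effects sit well inside the confidence intervals, and neither touches the primary endpoints or any test. The change is still worth making, because it is cheap and these rates are the study's longer-term safety results.

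**What to change.** Amend SAP 3.3 as follows.

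(a) Report stent thrombosis, numerator and denominator, among subjects with at least one stent implanted at the index procedure. Show the all-subject rate beside it and state the number stented.

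(b) Report 6- and 12-month MACE and stent thrombosis as Kaplan-Meier estimates with 95% confidence intervals, censored at last contact. State that deaths which are not endpoint events are censored. Cumulative incidence with such deaths as competing events is an acceptable alternative.

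(c) Show crude n/N beside these with a stated N: subjects who had the event or were followed to the opening of the visit window (day 180 − 30 = 150 and day 365 − 30 = 335). This N drops event-free losses and so leans upward. It is there for transparency, and the censored estimate is the one to read.

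The cost is SAP wording and a few extra tables. Stent implantation is already on the eCRF, adverse events are collected through 12 months, and SAP 7.3 already gives every adverse event an onset date. No endpoint definition, sample size or procedure changes. The stent thrombosis rate will look slightly less favourable, with a slightly wider interval.

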### **3.3.1 Hypotheses**

There is no specific hypothesis planned for this study.

### **3.3.2 Sample Size**

The study planned to enroll 100 patients with CTO lesions and will use BridgePoint Medical CTO System for treatment.

### **3.3.3 Statistical Methods**

All the Secondary Endpoints will be calculated by collecting patient follow-up information during and post procedure, at hospital discharge or at 30 days, 6 months and 12 months post procedure as described in the clinical trial schedule, using descriptive statistics to summarize continuous variables such as procedure time and X-ray time (such as mean, standard deviation, observed value, minimum and maximum value) and discontinuous variables (frequency table or percentage).

## **4 GENERAL STATISTICAL METHODS**

### **4.1 Analysis Sets**

All primary and Secondary endpoints will be analyzed both on an intent-to-treat (ITT) basis and on a per-protocol (PP) basis.

For intent-to-treat analyses, all patients who sign the IRB/IEC-approved study ICF and are enrolled in the study will be included in the analysis, regardless of whether or not a study device was implanted.

For per-protocol analyses, only patients who signed the IRB/IEC-approved study ICF and had used any component of BridgePoint Medical CTO System will be included in the analysis.

#### ***Effectiveness:***

Primary effectiveness analysis will include enrolled subjects that meet all inclusion/exclusion criteria and use any component of BridgePoint Medical CTO System (CrossBoss catheter, Stingray LP catheter or Stingray guidewire).

#### ***Safety:***

Safety analysis will include all enrolled subjects that use any component of BridgePoint Medical CTO System.

#### **4.2 Control of Systematic Error/Bias**

There is no randomization schema assigned in the study. The investigational devices/equipment shall be securely maintained, controlled, investigational device is used only by authorized/designated users and in accordance with this protocol and instructions/directions for use and used only in this clinical study.

#### **4.3 Number of Subjects per Investigative Site**

There are 5-10 Investigational sites in china, At least 100 subjects will be enrolled. Each site will be allowed to enroll up to a maximum of 25subjects.

### **5 ADDITIONAL DATA ANALYSES**

#### **5.1 Baseline Comparability**

Subject demographics, Physical assessment, Medical history, Angina assessment, LVEF, Cardiac medication, risk factors, and pre-procedure lesion characteristics will be summarized using descriptive statistics (e.g., mean, standard deviation, n, minimum, maximum) for continuous variables and frequency tables for discrete variables. No formal statistical testing will be done since this is a single-arm trial.

Lesion description both subject based and lesion based are also summarized with counts and percent for categorical data and descriptive statistics for continuous data. Pre-Procedural Lesion characteristics, and Post-Procedure Lesion characteristics are summarized and presented descriptively based on the data type.

#### **5.2 Medications**

Cardiac Medications are summarized with counts and percent for pre-procedure (<= 3 days & 14 days), Procedure, 30-days, 6-months and at 12-months. Antiplatelet medications are also summarized at pre-procedure(<=3 days), procedure, 30-days, 6-months and at 12-months with counts and percent.

#### **5.3 Subject Disposition**

Subject follow-up compliance summarized at 30-days, 6-months and 12-months' time with count and Subjects enrolled by site are summarized with counts.

#### **5.4 Adverse Events**

Non-serious AE's and SAE's will be summarized as the number of events and percentage of subject by MedDRA system organ class (SOC) and preferred term (PT). Frequency of site reported Serious adverse events and non-serious adverse events are presented. Also, procedure related serious and non-serious adverse events are summarized by SOC and PT. A listing based on deaths reported will also presented.

## **5.5 Protocol Deviations and Device Deficiencies**

The definitions of Major Protocol deviations (PD) and Minor Protocol deviations (PD) are detailed below:

- Major PD is a protocol deviation that directly or potentially disrupts the study progress (i.e., the study design, study data and results can be compromised), OR a protocol deviation that compromises the rights, safety and welfare of study participants
- Minor PD is a protocol deviation that does not disrupt study progress (i.e., the study design, study data and results will not be compromised), AND does not compromise the rights, safety and welfare of study participants.

Major Protocol deviations and Minor Protocol deviations will be summarized for all Deviation categories and planned events by percentage of Subjects and by percentage of deviations.

## **5.6 Device Deficiencies**

- Device deficiency is any inadequacy of a medical device with respect to its identity, quality, durability, reliability, safety or performance. Device deficiencies include malfunctions, use errors, and inadequate labeling.
- All the Device deficiencies will be categorized at all the procedural time points and will be summarized

## **5.7 Interim Analyses**

No formal Interim analysis are planned for this study.

## **5.8 Subgroup Analyses**

No Subgroup analysis are planned for this study.

## **5.9 Justification of Pooling**

This study will be conducted under a common protocol for each investigational site with the intention of pooling data for analysis. Every effort will be made to promote consistency in study execution at each investigational site.

## **5.10 Multivariable Analyses**

No multivariate analysis is included for the primary, secondary or other endpoints.

### **5.11 Other Analyses**

Clinical event rate will be expressed by percentage, and continuous variables will be expressed by number of samples, mean value, standard deviation, minimum and maximum value, where point estimation and 95% confidence limit will be provided.

### **5.12 Changes to Planned Analyses**

Any changes to the planned statistical analyses made prior to performing the analyses will be documented in a Statistical Analysis Plan approved prior to performing the analyses. Changes from the planned statistical methods after performing the analyses will be documented in the clinical study report along with a reason for the deviation and will be documented in the clinical study report.

## **6 VALIDATION**

All clinical data reports generated per this plan will be validated per 90702587, Global WI: Clinical Data Reporting Validation. The validation level R1 chosen for all primary, secondary, safety and other additional endpoints. The validation program includes checking logs and generating compare reports in comparing with main programming datasets. Statistical analyses and validation will be performed by IQVIA team.

## **7 PROGRAMMING CONSIDERATIONS**

All statistical programming tasks will be performed by IQVIA™ independently.

### **7.1 Statistical Software**

All statistical analyses will be done using The SAS System Version 9.2 software or above (Copyright © 2000 SAS Institute Inc., [name]. All rights reserved.).

### **7.2 Format of Output**

Results of analysis will be output programmatically to Microsoft Office® Word documents from SAS with no manual intervention. All output for the final statistical report will be in the form of a Word document containing tables, figures, graphs, and listings, as appropriate.

### **7.3 Methods for Handling Missing Data**

No imputation method will be performed for the missing data handling.

Missed or late visits will be recorded as Protocol Deviations.

When calculating rates of all adverse events, both device and/or procedure related with missing event date (i.e. mm/dd/yyyy), the ideal is to work with safety and/or data management representatives to query sites for missing data. However missing and partial missing dates may be handled as using the worst case scenario as follows:

Partial Date	Action Taken
Entire adverse event onset date is missing	The procedure date will be used for the onset date.
The month and the day of the month are missing but the year is available	January 1 st will be used for the month and day of the onset date. However, if the imputed date falls before the procedure date, then the procedure date will be used for the onset date.
Day is missing, but the month and year are available	The 1 st will be used as the day of the onset date. However, if the imputed date falls before the procedure date, then the procedure date will be used for the onset date.
